### **Data analysis**

The IBM Statistical Package for the Social Sciences (SPSS, version 29.0, NY, USA) will be performed to conduct all statistical analyses. For demographic data, continuous variables are represented by mean (standard deviations), while categorical variables are shown as frequencies (percentages). For the psychometric data, Cronbach's alpha coefficient and corrected item-total correlation will be used to assess **internal consistency** of the P-CIN. Cronbach's alpha value higher than 0.70 is acceptable with the interpretation as follows: below 0.70 = poor; between 0.70 and 0.79 = fair; between 0.80 and 0.89 = good; and above 0.90 = excellent.[25] Values for corrected item-total correlation can be explained as follows: values between 0 and 0.19 indicate that the item is not discriminating well, 0.2-0.39 indicate

good discrimination, 0.4 and above indicate very good discrimination. Good internal consistency reliability is indicated by a Cronbach's alpha coefficient  $\geq 0.70$  and item-total score correlations ranging from 0.30 to 0.70. The intraclass correlation coefficient (ICC) will be used to evaluate the **test-retest reliability**. For the results interpretation, minimum ICC values of 0.70 are considered satisfactory, values above 0.8 or 0.9 are often regarded as a sign of good or excellent test-retest reliability.[26] Concerning for the **content validity**, a scale with excellent content validity should be composed of I-CVIs of 0.78 or higher and UA -CVI/Ave-CVI of 0.8 and 0.9 or higher, respectively. Spearman's correlation coefficient ( $r$ ) will be performed to evaluate **convergent validity**. The correlation values for convergent validity are classified as follows:  $r=0$ , no correlation;  $r=0.10-0.29$  ( $-0.10$  to  $-0.29$ ), negligible correlation;  $r=0.30-0.49$  ( $-0.30$  to  $-0.49$ ), low positive (negative) correlation;  $r=0.50-0.69$  ( $-0.50$  to  $-0.69$ ), moderate positive (negative) correlation;  $r=0.70-0.89$  ( $-0.70$  to  $-0.89$ ), high positive (negative) correlation;  $r=0.90-1.00$  ( $-0.90$  to  $-1.00$ ), very high positive (negative) correlation.[27] Spearman's correlation coefficients equal to 0.70 or over are desirable. To determine **criterion validity**, Spearman's correlation coefficient will be used. Concerning the effectiveness diagnostic test, receiver operating characteristic (**ROC**) curve analysis will be performed. The interpretation of the **AUC** as follows: fail ( $0.5 \leq \text{AUC} < 0.6$ ), poor ( $0.6 \leq \text{AUC} < 0.7$ ), fair ( $0.7 \leq \text{AUC} < 0.8$ ), good ( $0.8 \leq \text{AUC} < 0.9$ ), excellent ( $0.9 \leq \text{AUC}$ ). **Youden's Index** will be used to calculate the optimal cut-off value. Concerning the CFA,  $\chi^2/\text{df}$  for value lower than 5 the fit is acceptable. RMR and SRMR: the lower the values, the better the fit. GFI and CFI values over 0.90 are considered a good fit (with a maximum value equal to 1). Reference value for the RMSEA between 0.05 to 0.08 mean the adjustment is good. Factor loading values above or close to 0.70 are better to explain the structure. As for the clinical feasibility, the P-CIN will be considered a practical tool for implementation in clinical practice settings if 80% or more of the children completed the questionnaire independently.

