The original P-CIN was developed in 2021 and the first electronic CIPN patient reported outcome measure (PROM). The European Organisation for Research and Treatment of Cancer Quality of Life Questionnaire - Chemotherapy-Induced Peripheral Neuropathy 20-item sub-scale (EORTC QLQ-CIPN20) served as a model when developing P-CIN specific items, and further validated in pediatric patients with CIPN in the United States. The P-CIN contains four items to rate CIPN subjective symptoms - numbness and tingling in the hands and feet. If pediatric patients reported experiencing these symptoms, they were directed to answer four additional questions regarding painful numbness and tingling. Five items were used to quantify CIPN functional deficits experienced such as picking up a penny or heel-

walking. Evidence indicates that the P-CIN is reliable and valid in United States context. However, there is a lack of measures for CIPN assessment in China after a systematic search and the P-CIN has never been validated for use with pediatric patients with CIPN in China. This lack of validated assessment measures preclude understanding the severity of the CIPN and hinders the development of appropriate interventions to promote CIPN symptoms management. On the other hand, a culturally sensitive assessment is critical in defining, identifying, describing and understanding the signs and symptoms of CIPN[3] as the culture and language can impact the expression and interpretation of symptom characteristics.[4] For instance, in East Asia, terms like “burning” were never used, with patients may report “numbness”.[4, 5] Due to the aforementioned concerns, it may be not appropriate to apply the P-CIN to assess the CIPN severity of pediatric patients before cross-cultural adaptation and validation. It is essential that assessment measures are appropriately adapted and validated in a new cultural setting to ensure valid and reliable measures.

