## **CIPN measurements**

### ***Pediatric chemotherapy-induced peripheral neuropathy (P-CIN)***

It was originally developed for children  $\geq$  6 years old who had received or were receiving neurotoxic chemotherapy and reported peripheral neuropathy to quantify numbness and tingling in the hands and feet and the functional deficits in the past two to three days[6]. The P-CIN comprises 13 items, with eight items to rate CIPN symptoms in the hands and feet and five items to rate the difficulty of performing functional tasks, e.g., standing on one leg and closing eyes for 15 seconds[6]. Each item is rated using a 6-point faces scale. The total score ranges from 0 to 65 with higher scores indicating more severe CIPN[6].

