***Wong-baker FACES Pain Rating scale***

This scale combines pictures and numbers to enable the user to rate pain which demonstrates six faces with increasing degree of pain from left to right, where each face is rated on a scale of 10 in which 0 indicated no hurt, 2 indicated hurts a little, 4 indicated hurts little more, 6 indicated hurts, even more, 8 indicated hurts a whole lot, 10 indicated hurts worst[18]. It can be used for children over the age of 3, and for adults[18]. This scale has adequate psychometric properties and it is easy and quick to[19] and it has been validated among Chinese children with acute fever[20].

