### ***Chinese version of the Pediatric Quality of Life Inventory (PedsQL) Cancer Module***

The PedsQL Cancer Module will be used to assess the participants' QoL. This scale contains 27 items grouping into eight subscales including (1) pain and hurt, (2) nausea, (3) procedural anxiety, (4) treatment anxiety, (5) worry, (6) cognitive problems, (7) perceived physical appearance, and (8) communication. There are parallel and identical versions for pediatric patients (young child: 5-7 years old, child: 8-12 years old, and adolescent: 13-18 years old) and parents (toddler: 2-4 years old plus the above three age groups). The participants rated how frequently a particular problem occurred in the past month, using a three-point Likert scale (0 = Never, 2 = Sometimes, 4 = Almost always) for children 5-7 years old and a five-point Likert scale (0 = Never, 1=Almost never, 2=sometimes, 3=often, 4 = Almost always) for children of 8-18 years old and for the parents of patients of all ages. Each item score will be reversely scored and then linearly transformed into 0-100 scale (0 = 100, 1 = 75, 2 = 50, 3 = 25, 4 = 0). The scale is the average of the total item scores. Higher scores represent better quality of life (QoL). The psychometric properties of the Chinese version of the scale have been well-examined[21]. This scale has been demonstrated as a valid and reliable tool in assessing QoL for Hong Kong Chinese adolescent with cancer[21].

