### ***Validity assessment***

Validity refers to an instrument measures exactly what it proposes to measure. Validity can be assessed in different forms such as content validity, convergent validity, criterion validity, and construct validity. **Content validity** can be defined as the extent to which an assessment tool accurately and fully reflects the concept being measured. The Delphi technique will be used to establish the content validity of the P-CIN. We will obtain the opinions of 10 experts through a structured questionnaires delivered two iterations until consensus will be reached. **Convergent validity** is the degree to which scores on a measure associate with scores on other measures that are intended assess similar constructs. Pain level, self-reported quality of life are CIPN-related concepts that have been identify pediatric oncology patients with CIPN risk[15]. Therefore, convergent validity will be explored using well-established CIPN-related measurements, namely, (1) the Wong-baker FACES pain rating scale to assess levels of pain; and (2) the Pediatric Quality of Life Inventory (PedsQL) Cancer Module to determine level of quality of life with the help of the Spearman's correlation coefficient (r). **Criterion validity** is the relation between the score of a certain instrument and some external criterion. This criterion has to be a widely accepted measure, with the same characteristics of the assessment tool. Criterion validity will be evaluated using the pediatric neurologists' CIPN diagnosis as a reference criterion. Spearman's correlation coefficient (r) will be calculated to evaluate the correlations between the P-CIN and the CIPN diagnosis. Using diagnostic testing to determine the presence or absence of the CIPN is essential. The ROC curve aims to find an optimal cut-off value with the best CIPN diagnostic performance. Additionally, the ROC curve is utilized to evaluate the overall diagnostic performance of a test and to compare multiple diagnostic tests.[23] The area under the curve (AUC) will be used to measure the accuracy of diagnostic test. Generally, an  $AUC \geq 0.8$  is considered acceptable. Youden statistic (calculated as sensitivity + specificity - 1) was used to determine the optimal cut-off value.[24] The point at which this value is maximized is determined as the optimal cut-off value.[24]

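### The convergent-validity benchmark of 0.70 has no expected direction, and one demanding level is set for two comparators that the protocol calls only related to neuropathy

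*Protocol*

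**What the plan says.** The Protocol's Validity assessment section plans to explore convergent validity with Spearman correlations between P-CIN and two comparators: the Wong-Baker FACES pain scale and the PedsQL Cancer Module. It justifies them thus: "Pain level, self-reported quality of life are CIPN-related concepts".

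The Data analysis section first gives descriptive bands. Each covers positive and negative values of the same size. For example, 0.70 to 0.89 and its negative mirror image are both labelled "high positive (negative) correlation". It then adds: "Spearman's correlation coefficients equal to 0.70 or over are desirable". No other level is named as a target for convergent validity, and neither section states an expected sign.

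The scoring directions are given elsewhere:

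- P-CIN: "The total score ranges from 0 to 65 with higher scores indicating more severe CIPN".
- PedsQL Cancer Module: "Higher scores represent better quality of life (QoL".
- Wong-Baker: one six-face item, "where each face is rated on a scale of 10", with 10 the worst pain.

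**The concern.** A convergent-validity hypothesis needs a direction and a size. The benchmark sentence gives a size only, and the two comparators are expected to move in opposite directions. Nothing stated would count a positive correlation of 0.70 with PedsQL (worse neuropathy going with better quality of life) as evidence against P-CIN.

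The size is a separate problem. A level of 0.70 suits two measures of one construct, but pain and quality of life are presented only as related concepts. If the constructs are clearly but not almost perfectly related, a sound translation would probably be described as short of the desirable level. The sign and level that count as support would then have to be settled after the data are seen.

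**Working it through.** **1. Expected sign, from the scoring rules**

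| Comparator | High score means | Expected sign with P-CIN (high = worse) |
|---|---|---|
| Wong-Baker | more pain | positive |
| PedsQL Cancer Module | better quality of life | negative |

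Read literally, 0.70 or over can be met by PedsQL only in the wrong direction. Read as an absolute value, it is met by −0.70 and equally by +0.70. Neither reading tests direction.

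**2. Overlap of content**

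- P-CIN has eight symptom items and five functional-task items, with recall of two to three days. Four of the 13 items concern painful symptoms and are conditional: children who reported numbness or tingling were the ones for whom "they were directed to answer four additional questions regarding painful numbness and tingling".
- Wong-Baker is a single rating of pain.
- For PedsQL, "This scale contains 27 items grouping into eight subscales": pain and hurt, nausea, procedural anxiety, treatment anxiety, worry, cognitive problems, physical appearance and communication. Only the first lies close to neuropathy. Recall is one month.

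**3. What an observed 0.70 requires**

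The 0.70 level has no derivation in the Protocol, so there is no figure to reproduce. No expected correlations and no comparator reliabilities are given either, so the reliabilities below are assumptions. The Protocol's minimum of 0.70 for alpha and ICC applies to P-CIN only.

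Attenuation: observed r = latent r × √(rel₁ × rel₂), so the latent r needed is 0.70 / √(rel₁ × rel₂). Under bivariate normality, Spearman = (6/π) × arcsin(r/2). A Spearman of 0.70 then corresponds to r = 2 × sin(0.70π/6) = 0.717, which gives the last column.

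| Reliabilities | √(rel₁ × rel₂) | Latent r needed | With Spearman conversion |
|---|---|---|---|
| 0.70, 0.70 | 0.700 | 1.00 | 1.02 (not attainable) |
| 0.80, 0.80 | 0.800 | 0.875 | 0.90 |
| 0.85, 0.80 | 0.825 | 0.85 | 0.87 |
| 0.90, 0.90 | 0.900 | 0.78 | 0.80 |

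**4. Chance of observing 0.70 or more in the expected direction**

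Take n = 300 (Protocol, Sample size) and assume complete data. Use Fisher z with SE = √((1 + ρ²/2)/(n − 3)), where ρ is the true Spearman. For ρ = 0.60: SE = √(1.18/297) = 0.0630, and (0.8673 − 0.6931)/0.0630 = 2.76, so the chance is 0.3%.

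| True Spearman (absolute) | Chance |
|---|---|
| 0.50 | about 1 in 10 million |
| 0.60 | 0.3% |
| 0.65 | 7% |
| 0.70 | 50% |
| 0.75 | 95% |
| 0.80 | 99.97% |

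**5. Dependence on the assumptions**

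This combines steps 3 and 4. The last column also shows the result with the alternative variance 1.06/(n − 3), where it differs.

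| Latent r | Reliabilities | Expected Spearman | Chance of ≥ 0.70 |
|---|---|---|---|
| 0.6 | 0.85, 0.80 | 0.48 | below 0.01% |
| 0.8 | 0.85, 0.80 | 0.64 | 5% (4%) |
| 0.8 | 0.90, 0.90 | 0.70 | 54% |
| 0.9 | 0.85, 0.80 | 0.73 | 79% (81%) |

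The level is demanding but attainable if the latent correlation is very high.

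**The case against.** The strongest reply on sign is that the bands sit immediately before the benchmark and treat negative and positive coefficients of the same size alike. The authors evidently foresaw negative correlations, so size is the natural reading. That stands. A reader might infer that PedsQL cannot meet the target in the right direction, but this follows only if the sentence is isolated from the bands. The bands label size, however, and do not say which sign supports validity.

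On consequences, the word used is desirable. Nothing says that P-CIN fails below 0.70, and values from 0.30 to 0.69 have their own labels, low and moderate. Where the Protocol wants a decision rule it writes one, as with the 80% independent-completion criterion for feasibility. This also stands, so it would be wrong to infer that a valid P-CIN would be declared invalid. It could be reported as below the only level named as desirable, which is a weaker consequence but a real one.

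On pain, four of the 13 items concern painful symptoms, and high reliabilities or a latent correlation of 0.9 bring 0.70 within reach (step 5). A reader might infer that the target is out of reach for pain; the documents do not show that.

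Finally, detailed hypotheses and intervals are often left to a statistical analysis plan, and one may exist. But the Protocol itself fixes this benchmark, so the point concerns a stated level and not an omission.

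**Conclusion.** The point holds as a badly specified benchmark. That the expected PedsQL correlation is negative follows from the Protocol's own scoring rules and needs no assumption; nor does the absence of any stated direction. That 0.70 is demanding rests on the comparators being described only as related, on the content and recall differences, and on assumed reliabilities of 0.70 to 0.90. Over that range the latent correlation must be about 0.78 or higher. A true Spearman of 0.60 to 0.65 would reach the level in only 0.3% to 7% of studies of this size.

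Data collection and the coefficients themselves are unaffected. What changes is the conclusion the study can draw about convergent validity. It should be corrected before analysis.

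**What to change.** In the Data analysis section, replace the benchmark sentence with one prespecified hypothesis per comparator:

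- **Direction:** positive for Wong-Baker, negative for the PedsQL Cancer Module.
- **Size:** a level justified for related constructs. One option is at least the low band of the Protocol's own scheme, an absolute value of 0.30 or more.
- **Reporting:** each Spearman coefficient with its 95% confidence interval, and a statement that a correlation in the opposite direction does not support validity.

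Do not keep 0.70 for either comparator unless a reason is given for expecting it.

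The cost is one paragraph, with no new data or assessments. The drawback is that the stated target becomes less ambitious, so the chosen level should be justified and fixed before the data are examined.

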### **Ethical considerations**

This study will not involve any invasive procedure, thus the chance of imposing physical harms on subjects is minimal. If there is any adverse effects that happens during the data collection, the registered nurses will immediately stop and ask the participants whether they would like to continue or terminate the study. With parental consent, we will pass their contact to the head nurses of pediatric oncology ward (our co-investigators). They will further assess the psychological well-being of the participants. If necessary, they will refer these participants to relevant medical personnel, e.g. doctors, clinical psychologists and/or social workers to follow-up.

